7.9.3. Additional Outcome Measures

1. All-cause mortality at one year, and annually through 10 years

Event rate estimates will be provided at 1 year and annually thereafter up to 10 years for the attempted implant set. The outcome is descriptive including Kaplan-Meier rates and no statistical hypothesis test is specified.

2. All stroke (disabling and non-disabling) at one year, and annually through 10 years

Event rate estimates will be provided at 1 year and annually thereafter up to 10 years for the attempted implant set. The outcome is descriptive including Kaplan-Meier rates and no statistical hypothesis test is specified.

3. New permanent pacemaker implantation at 30 days

Event rate estimates will be provided at 30 days for the attempted implant set. The outcome is descriptive including Kaplan-Meier rates and no statistical hypothesis test is specified.

4. Myocardial Infraction at 30 days

Event rate estimates will be provided at 30 days for the attempted implant set. The outcome is descriptive including Kaplan-Meier rates and no statistical hypothesis test is specified.

5. Life-threatening bleeding at 30 days, one year, and annually through 10 years

Event rate estimates will be provided at 30 days, 1 year and annually thereafter up to 10 years for the attempted implant set. The outcome is descriptive including Kaplan-Meier rates and no statistical hypothesis test is specified.

6. Prosthetic valve endocarditis at 30 days, one year, and annually through 10 years

Event rate estimates will be provided at 30 days, 1 year and annually thereafter up to 10 years for the attempted implant set. The outcome is descriptive including Kaplan-Meier rates and no statistical hypothesis test is specified.

7. Prosthetic valve thrombosis at 30 days, one year, and annually through 10 years

Event rate estimates will be provided at 30 days, 1 year and annually thereafter up to 10 years for the attempted implant set. The outcome is descriptive including Kaplan-Meier rates and no statistical hypothesis test is specified.

8. Valve-related dysfunction requiring repeat procedure at 30 days, one year, and annually through 10 years

Event rate estimates will be provided at 30 days, 1 year and annually thereafter up to 10 years for the attempted implant set. The outcome is descriptive including Kaplan-Meier rates and no statistical hypothesis test is specified.

9. Repeat hospitalization for ascending aorta disease at 30 days, one year, and annually through 10 years

Event rate estimates will be provided at 30 days, 1 year and annually thereafter up to 10 years for the attempted implant set. The outcome is descriptive including Kaplan-Meier rates and no statistical hypothesis test is specified.

10. Repeat hospitalization for aortic valve disease at 30 days, one year, and annually through 10 years

Event rate estimates will be provided at 30 days, 1 year and annually thereafter up to 10 years for the attempted implant set. The outcome is descriptive including Kaplan-Meier rates and no statistical hypothesis test is specified.

11. Hemodynamic performance metrics by Doppler echocardiography
 - a. Mean aortic gradient at baseline, 30 days, one year, annually through 5 years and at years 7 and 10
 - b. Effective orifice area at baseline, 30 days, one year, annually through 5 years and at years 7 and 10
 - c. Degree of total, peri, and transvalvular prosthetic regurgitation at baseline, 30 days, one year, annually through 5 years and at years 7 and 10

The echocardiographic measurements will be reported at each of the specified time points for the implanted set with Echo data. No statistical hypothesis test is specified.

For mean gradient and effective orifice area, the descriptive statistics (mean, median, standard deviation, minimum, maximum and interquartile ranges) will be presented.

Prosthetic regurgitation severity will be reported as proportions at each specified time point.

12. New York Heart Association (NYHA) functional classification at baseline, 30 days, one year and annually through 5 years and at years 7 and 10

NYHA classifications will be summarized with frequencies and percentages at baseline, 30 days, 1 year, and annually through 5 years and at years 7 and 10. All attempted implant subjects with available NYHA collections (I/II/III/IV) will be included in the analysis. No statistical hypothesis test is specified.

13. Health-related quality of life as assessed by
 - a. Kansas City Cardiomyopathy (KCCQ) instrument at baseline, 30 days, one year, annually through 5 years
 - b. EQ-5D survey at baseline, 30 days and one year

The KCCQ, EQ-5D will be summarized with means, medians, standard deviations, minimums, maximums, and interquartile ranges, at each specified time point for the attempted implant set. No statistical hypothesis test is specified.

7.10.Changes to Planned Analysis

The planned analyses in this SAP are aligned with the planned analyses noted in the CIP.

8. Validation Requirements

Level 1 validation (independent validation) will be used for the analysis datasets and the primary endpoints. Level 1 or 2 validation (peer review) will be used for additional analyses, data summaries, and listings.

9. References

NA

10. Statistical Appendices

There are no statistical appendices for this study.

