#### Additional Outcome Measures

Additional outcome measures are listed below.

1. All-cause mortality at one year, and annually through 10 years
2. All stroke (disabling and non-disabling) at one year, and annually through 10 years
3. New permanent pacemaker implantation at 30 days
4. Myocardial infarction at 30 days
5. Life-threatening bleeding at 30 days, one year, and annually through 10 years
6. Prosthetic valve endocarditis at 30 days, one year, and annually through 10 years
7. Prosthetic valve thrombosis at 30 days, one year, and annually through 10 years
8. Valve-related dysfunction requiring repeat procedure at 30 days, one year, and annually through 10 years
9. Repeat hospitalization for aortic valve disease at 30 days, one year, and annually through 10 years
10. Repeat hospitalization for ascending aorta disease at 30 days, one year, and annually through 10 years
11. Hemodynamic performance metrics by Doppler echocardiography
  - Mean aortic gradient at baseline, 30 days, one year, annually through 5 years and at years 7 and 10
  - Effective orifice area at baseline, 30 days, one year, annually through 5 years and at years 7 and 10
  - Degree of total, peri, and transvalvular prosthetic regurgitation at baseline, 30 days, one year, annually through 5 years and at years 7 and 10
12. New York Heart Association (NYHA) functional classification at baseline, 30 days, one year and annually through 5 years and at years 7 and 10  
NYHA function classification will be reported as proportions at each specified time point.
13. Health-related quality of life as assessed by

- Kansas City Cardiomyopathy (KCCQ) instrument at baseline, 30 days, one year, annually through 5 years
- EQ-5D survey at baseline, 30 days and one year

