### 7.3. Inclusion Criteria

1. Prospective subjects must meet all of following inclusion criteria to be eligible for implantation:

- Severe aortic stenosis, defined as follows:
  - a) For symptomatic patients:  
Aortic valve area  $\leq 1.0 \text{ cm}^2$  (or aortic valve area index of  $\leq 0.6 \text{ cm}^2/\text{m}^2$ ), **OR** mean gradient  $\geq 40$  mmHg, **OR** Maximal aortic valve velocity  $\geq 4.0$  m/sec by transthoracic echocardiography at rest
  - b) For asymptomatic patients:  
Very severe aortic stenosis with an aortic valve area of  $\leq 1.0 \text{ cm}^2$  (or aortic valve area index of  $\leq 0.6 \text{ cm}^2/\text{m}^2$ ), **AND** maximal aortic velocity  $\geq 5.0$  m/sec, or mean gradient  $\geq 60$  mmHg by transthoracic echocardiography at rest, **OR**

Aortic valve area of  $\leq 1.0 \text{ cm}^2$  (or aortic valve area index of  $\leq 0.6 \text{ cm}^2/\text{m}^2$ ), **AND** a mean gradient  $\geq 40 \text{ mmHg}$  or maximal aortic valve velocity  $\geq 4.0 \text{ m/sec}$  by transthoracic echocardiography at rest, **AND** an exercise tolerance test that demonstrates a limited exercise capacity, abnormal BP response, or arrhythmia **OR**

Aortic valve area of  $\leq 1.0 \text{ cm}^2$  (or aortic valve area index of  $\leq 0.6 \text{ cm}^2/\text{m}^2$ ), **AND** mean gradient  $\geq 40 \text{ mmHg}$ , or maximal aortic valve velocity  $\geq 4.0 \text{ m/sec}$  by transthoracic echocardiography at rest, **AND** a left ventricular ejection fraction  $< 50\%$ .

2. Patient is considered low risk for SAVR, where low risk is defined as predicted risk of mortality for SAVR  $< 3\%$  at 30 days per multidisciplinary local heart team assessment.
3. Bicuspid aortic valve anatomy (all sub-types) confirmed by MDCT.
4. The subject and the treating physician agree that the subject will return for all required post-procedure follow-up visits.

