7.4. Handling of Missing, Unused, and Spurious Data and Dropouts

Every effort will be undertaken to minimize missing data. In time-to-event outcomes drop-outs will be censored at the time of discontinuation, consistent with the Kaplan-Meier approach.

Missing (accidentally, due to withdrawal, missing follow-up or loss to follow-up, etc.), unused and spurious data will remain identifiable in the database. Data from subjects that cannot be analyzed for a specific variable will be displayed as missing in the relevant summary tables. In this manner, all data for a specific variable are accounted for. Unless otherwise specified, no statistical techniques will be used to impute missing data. The number of subjects included in each analysis will be reported so that the reader can assess the potential impact of missing data.

In the case of partial dates, if only the month and year are known, the event or assessment will be analyzed as if it occurred on the 15th of that month. If only the year is known, the event or assessment will be analyzed as if it occurred on June 30th of that year. These resolutions of partial dates are subject to the restrictions that events must occur no earlier than the procedure date.

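### NYHA, KCCQ and EQ-5D are summarised visit by visit with no comparison to the same subjects' baseline, so selective loss can look like improvement at later visits

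*SAP*

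**What the plan says.** SAP 7.9.3 item 12: "NYHA classifications will be summarized with frequencies and percentages at baseline, 30 days, 1 year", and then at later visits to year 10. The denominator is given as "All attempted implant subjects with available NYHA collections (I/II/III/IV) will be included in the analysis". Protocol 4.1 agrees: "NYHA function classification will be reported as proportions at each specified time point".

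SAP 7.9.3 item 13, on the attempted implant set: "The KCCQ, EQ-5D will be summarized with means, medians, standard deviations, minimums, maximums, and interquartile ranges, at each specified time point". KCCQ runs to year 5 and EQ-5D to one year.

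SAP 7.4: "Unless otherwise specified, no statistical techniques will be used to impute missing data". The same section offers some help: "The number of subjects included in each analysis will be reported so that the reader can assess the potential impact of missing data".

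Protocol 8.1 requires all three measures before the procedure. Neither the outcome lists (Protocol 4.1 and 12.7, SAP 7.9.3) nor SAP 7.2 mentions change from baseline, a shift table or a category for death for these measures.

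Protocol 8.5 limits what is collected after a failed or reversed implant. A subject taken to the procedure room who receives no valve is tracked for safety only, to day 30. A subject whose valve is explanted is tracked for safety only, for 30 days after the explant.

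**The concern.** Each visit's percentage or mean describes a different group of people. Someone who has died, been explanted or stopped attending contributes to the baseline column but not to the later one. Part of this loss is tied to outcome by design, because death and explant both end collection. If those who leave started out worse, the later columns look better than the baseline column even when nobody has changed.

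This matters because the study has no control arm. The course from baseline is the only internal description of symptoms and quality of life, and readers will take the difference between columns as improvement. If a paired result is produced later, its definition and denominator will have been chosen after the data were seen, which the SAP exists to prevent.

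**Working it through.** The documents give no baseline NYHA mix, KCCQ mean, dropout rate or share of asymptomatic subjects, so there is no stated figure to reproduce. The inputs below are assumptions unless a source is named.

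**Shift in a mean when nobody changes.** Let μ be the baseline mean of all subjects, m the fraction missing at a visit, and d the baseline deficit of the missing against all subjects. The mean of those remaining is [μ − m(μ − d)]/(1 − m) = μ + m·d/(1 − m), so the artefact is m·d/(1 − m). If d is measured against those remaining, the artefact is m·d.

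- m = 0.10, d = 10: 1.0/0.90 = 1.1 KCCQ points
- m = 0.10, d = 20: 2.0/0.90 = 2.2
- m = 0.20, d = 10: 2.0/0.80 = 2.5
- m = 0.20, d = 20: 4.0/0.80 = 5.0
- Near 30 days, taking m = 0.024 (the weighted 30-day rate of death or disabling stroke in SAP Table 1, used as a stand-in for loss): 0.24/0.976 = 0.2 to 0.48/0.976 = 0.5
- d = 0: no shift at any m

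Paired change in the same subjects is exactly 0 in every one of these cases.

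**Shift in the NYHA I/II share when nobody changes.** Let p be the baseline III/IV share, L the overall loss, and rr the ratio of loss in III/IV to loss in I/II. Loss in I/II is l0 = L/(1 − p + p·rr), and the displayed I/II share is (1 − p)(1 − l0)/(1 − L). With p = 0.20, L = 0.20 and rr = 2, l0 = 0.20/1.20 = 0.167 and the share is 0.80 × 0.833/0.80 = 83.3%, against 80% at baseline. Over p = 20 to 30% and rr = 2 to 3, the rise is:

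- L = 2.4%: 0.3 to 0.6 percentage points
- L = 10%: 1.5 to 2.9
- L = 20%: 3.3 to 6.6
- L = 40% (a late visit): 8.9 to 17.5
- rr = 1: 0 throughout

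**Cross-check on KCCQ.** Put the same two-group model on the KCCQ scale, with assumed baseline means of 50 in III/IV and 75 in I/II. At 20% loss the mean rises 0.8 to 1.6 points. The implied deficit against all subjects is shift × (1 − m)/m, that is 0.83 × 4 = 3.3 to 1.64 × 4 = 6.6 points. A deficit of 10 to 20 points therefore needs stronger selection than this model gives, and 5.0 should be read as an upper value.

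**Non-implanted subjects.** If the subject and implant columns of SAP Table 1 are read as attempted and implanted, 4 of 301 in one study and none in the other three were not implanted: 4/(391 + 301 + 60 + 60) = 4/812 = 0.5%, or about 0.7 of 150. Most later loss would come from death, explant and dropout.

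**NYHA denominator.** Protocol 7.3 also admits subjects under "For asymptomatic patients". Anyone in class I at entry cannot improve in class. If 10 to 30% (15 to 45 of 150) enter in class I and 70% of the rest improve, the share improved among all is 0.90 × 70 = 63% to 0.70 × 70 = 49%. Both denominators are legitimate, but the planned tables allow neither.

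**The case against.** These are the last two of 13 additional outcomes, all descriptive, in a study whose objective is procedural and assessed at 30 days. There the shift is 0.2 to 0.5 KCCQ points or 0.3 to 0.6 percentage points. EQ-5D stops at one year, so a year-5 illustration says little about it. The SAP already counts deaths, explants, withdrawals and completed visits (7.1.1), shows missing data and N (7.4), reports Kaplan-Meier mortality annually (7.9.3), and sets baseline beside follow-up. All this stands. None of it shows the baseline status of those missing at a visit, so a reader still cannot recover change in the same subjects.

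The documents do not support four stronger readings that a reader might infer:

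- That later means must rise. No section says those lost are sicker. Death and explant make it plausible, while the low-risk criterion and the life-expectancy exclusion limit early loss.
- That asymptomatic entrants cannot gain on KCCQ or EQ-5D. One entry route in Protocol 7.3 rests on an abnormal exercise test, which may show limited capacity. The strict ceiling applies only to NYHA class I.
- That such entrants distort the mean. If 10% gain nothing and the rest gain 20 points, 18 is the true mean gain in the enrolled population, and paired change also gives 18.
- That pairing improves on a planned standard error. The SAP plans no difference of visit means to compare it with.

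**Conclusion.** The point holds for later visits, mainly NYHA beyond one year and KCCQ towards year 5. As planned, a better picture there can be individual change, selective loss or both, and the tables cannot separate them. The size is about 1.1 to 5.0 KCCQ points at 10 to 20% missing with a 10 to 20 point deficit, and 3.3 to 6.6 percentage points of NYHA I/II share at 20% loss. Every input is assumed, and the direction depends on the lost subjects having been worse at baseline. No primary endpoint, decision rule or sample size is affected. This is a worthwhile, nearly free improvement to a descriptive analysis, not a correction of an error.

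**What to change.** In SAP 7.9.3:

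- Item 13: at each post-baseline visit at which the instrument is collected, add paired change from baseline with a 95% confidence interval for KCCQ and EQ-5D, and show the baseline mean of those same subjects and their number.
- Item 12: add a shift table of baseline class by class at each visit, with separate columns for dead and missing. State the proportion improved by at least one class among subjects in NYHA II to IV at baseline.
- Optional: repeat by symptomatic or asymptomatic entry route, accepting that the asymptomatic group may be small.

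Keep the per-visit summaries. The cost is SAP wording and a few tables, with no new assessment and no hypothesis test. Paired change does not recover the outcomes of those lost, and it describes only subjects seen at both times. The dead and missing columns are there to keep that visible for NYHA.
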